## 6.3.2 Efficacy Analysis

Descriptive statistics for CFA%, duodenal pH, MBT and QOL outcomes (mean, standard deviation, median, range, 95% CI) will also be calculated for the total group comparing on and off omeprazole treatment using pair t-tests or Wilcoxon sign rank tests as appropriate. Changes within randomization groups over time will also be explored using paired t tests Differences between randomization groups (12 randomized initially to placebo vs. 12 to omeprazole treatment) on visit 1 will also be tested using unpaired t tests or Mann Whitney U rank sum test as appropriate. Significance of the differences on and off treatment assessed with paired t tests or Wilcoxon sign rank tests as appropriate. PK parameters can then be compared for the total group comparing on and off omeprazole treatment using pair t-tests or Wilcoxon sign rank tests as appropriate, and between randomization groups at each time point using an unpaired t-test or Mann Whitney U rank sum test as appropriate. Alternately, population PK analyses for repeated-measures endpoints can be conducted via nonlinear mixed-effects modeling with a qualified installation of the nonlinear mixed-effects modeling (NONMEM) software, Version VII, Level 2.0 (ICON Development Solutions, Hanover, MD). HA and PA concentrations will be transformed to molar quantities and the ratios for HA to PA Cmax and AUC and the associated 95% confidence interval will be calculated. A mixed-effects modeling approach will be employed to examine the correlation of subject characteristics (age, BMI, sex, disease status, etc) to CFA%, duodenal pH, QOL parameters and to PA and HA exposure metrics derived from the non-compartmental analysis to assess change over time in MBT response to PERT administration in subjects with CP. Metrics to be tested will be CFA%, duodenal pH, QOL parameters, PA and HA Cmax, AUC, HA/PA Cmax and AUC ratio and the %HA response comparing subjects when on or off omeprazole treatment and also comparing randomization groups at each time point. A value of p<0.05 will be considered statistically significant.

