	Visit 2 : Outcomes are measured after the 28 days of treatment or placebo; subjects then cross over to other treatment arm.
	Visit 3 : Outcomes are again measured after another 28 days of treatment or placebo. Once 72-hour stool collection is completed, subjects complete the study and return to normal medication regimen.
Efficacy Evaluations	The efficacy of PPI as adjunct to PERT will be evaluated using the gold standard CFA, as well as the MBT and the SmartPill®.
Pharmacokinetic Evaluations	N/A
Safety Evaluations	Safety will be monitored by adverse events reporting. The frequencies of AEs by type, body system, severity and relationship to study supplement will be summarized. SAEs (if any) will be described in detail.
Statistical And Analytic Plan	Comparison of outcomes by randomization group at each time point: Descriptive statistics for CFA%, duodenal pH and MBT outcomes (mean, standard deviation, median, range, 95% CI) will be calculated and for the total group comparing on and off omeprazole treatment using pair t-tests or Wilcoxon sign rank tests as appropriate. Differences between randomization groups at each time point and differences in the change over time with treatment will be assessed with unpaired t tests or Mann Whitney U rank sum tests as appropriate. For the MBT outcomes, a moment-based pharmacokinetic (PK) analysis will be performed based or non-compartmental methodology using WinNonLin version 9.1 (Pharsight, Cary, NC). Baseline (CO) and maximum (Cmax) plasma concentrations are calculated, and area under the curve from time zero to eight hours (AUC) is calculated using the linear trapezoid method. PK parameters can then be compared for the total group comparing on and off omeprazole using paired t-tests or Wilcoxon sign rank tests as appropriate, and between randomization groups at each time point using an unpaired t-test or Mann Whitney U rank sum test as appropriate. A mixed effects modeling approach will be employed to examine the correlation of subject characteristics (age, BMI, sex, disease status, etc) to CFA%, duodenal pH and to PA and HA exposure metrics derived from the non-compartmental analysis to assess change over time in MBT response to PERT administration in subjects with CP. Metrics to be tested will be CFA%, PA and HA Cmax, AUC, HA/PA Cmax and AUC ratio and the %HA

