## 3.1.3 Second Treatment Phase

After completing the second study visit, there will be a 14-day washout period during which subjects will discontinue their study medication but continue their standard diet/PERT use. Subjects will then cross over to the other treatment arm and undergo an additional 28 days of treatment with omeprazole or placebo. At the end of this treatment period, they will have a third study visit that will include the outcome measure assessments.

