## 5.2 Efficacy Evaluations

#### 5.2.1 Diagnostic Tests, Scales, Measures, etc.

Coefficient of Fat Absorption (CFA): The primary outcome, the coefficient of fat absorption (CFA%) will be determined by the 72-hour stool collections at Visits 2 and 3, and a 3-day weighed food record collection while consuming a moderate fat (about 80+ g/day) diet. These stool collections will be performed at home and returned to CHOP. Subjects will be given a home collection kit and detailed instructions. Specimens will be stored frozen until analysis of total fat content by a gravimetric method (Mayo Medical Laboratories, Rochester, MN). Total dietary intake of fat during the 3-day period will be assessed from the 3-day weighed food records which will coincide with the 72-hour stool collection, and the CFA% will be calculated. The CFA% will be compared between subjects on PPI and PERT versus PERT and placebo.

Malabsorption Blood Test (MBT): The MBT primary outcomes consist of parameters from pharmacokinetic analyses. The MBT consists of a simultaneous oral dose of pentadecanoic acid (PA), a free fatty acid, and triheptadecaenoin (THA), a triglyceride with three heptadecanoic (HA) saturated fatty acids requiring hydrolysis by pancreatic lipase before HA can be intestinally absorbed (Patent # US 7402405 B2, July 22, 2008). The MBT with the PA and THA is delivered in a breakfast test meal after a 12-hour fast and 24 hours without dairy foods. Serum concentration levels of PA and HA are assessed by gas-liquid chromatography (GC), from serum samples drawn prior to MBT and then hourly for eight hours. The MBT test meal is prepared immediately before consumption, with 5.0g of PA

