#### 6.3 Statistical Methods

#### 6.3.1 Baseline Data

Descriptive statistics for CFA%, duodenal pH, MBT, and QOL outcomes (mean, standard deviation, median, range, 95% CI) will be calculated at baseline for the total group for continuous variables and  $\chi$ -squared or Fisher's exact tests for categorical variables. Differences between randomization groups at each time point and differences in the change over time with treatment will be assessed with unpaired t tests or Mann Whitney U rank sum tests as appropriate. For the MBT outcomes, a moment-based pharmacokinetic (PK) analysis will be performed based on non-compartmental methodology using WinNonLin version 9.1 (Pharsight, Cary, NC). Baseline ( $C_0$ ) and maximum ( $C_{max}$ ) plasma concentrations are calculated, and area under the curve from time zero to eight hours (AUC) is calculated using the linear trapezoid method. To describe HA exposure relative to that of PA, the ratio of the HA to PA  $C_{max}$  ( $C_{max}$  HA/PA) and AUC (AUC HA/PA) is calculated for each subject after molar transformation and dose-normalization of exposure metrics. Using this method, population PK modeling is conducted by simultaneously fitting structural PK models to both PA and HA concentrations.

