## 6.4 Sample Size and Power

The primary hypotheses of this study: 1) The use of omeprazole, a proton pump inhibitor medication, in combination with PERT will significantly improve dietary fat absorption compared to placebo in subjects with CF and EPI as indicated by CFA%. Our previous experience in subjects with CF and EPI receiving PERT, CFA% was 81±14% in one study, 83±10% in another, and more recently, 89.5±7.4% in subjects with CF gating mutations and EPI. In comparison, in healthy subjects, CFA% is typically ≥93%. In the study of subjects with gating mutations in which CFA% was assessed before and after 3- months of ivacaftor treatment, there was a significant increase in CFA% of 3.1±3.0% (p<0.01) with ivacaftor treatment in the 15 subjects with EPI and were receiving PERT during the study.

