There is limited evidence from randomized placebo-controlled trials that agents such as omeprazole that reduce gastric acidity, when used as adjunctive therapy with PERT are associated with improvement in fat absorption. Heijerman and colleagues, in a randomized controlled trial with a crossover design, found a reduction of 4.8% in fecal fat excretion in 11 subjects receiving 14-days of omeprazole compared to when they received 14-days of placebo (18.1 % vs. 22.9%, respectively). In another study using a similar crossover design, the same authors found a reduction in fecal fat excretion of 8.9%, from 19.6% after 14-day placebo treatment to 10.7% after 14-day omeprazole treatment in 9 subjects on high dose pancreatic enzyme therapy. Proesmans et al, using a randomized crossover design in a study of 15 children with CF and confirmed steatorrhea, found a reduction 7.5 g of fecal fat (from 13.0 to 5.5 g) and an increase in CFA of 7% (from 87 to 94%) after one month of omeprazole use. In other clinical trials of H2 acid blockers as adjunctive therapy to PERT, CFA% improved from 77.1 to 83.6% in a study of 10 children with CF receiving PERT only, compared to PERT plus cimetidine over 14-day periods, and from 74.4% to 87.3% in 10 CF children receiving PERT only and PERT plus famotidine over 6-month periods. In our proposed randomized controlled trial with a crossover design, 22 subjects (11 randomized to 28-day treatment and 11 to placebo at Visit 1, then crossing over to the alternate treatment for 28-days) will have 80% power to detect an increase of 3% with omeprazole treatment compared to no change (0%) when on placebo with a common SD of 5% using a paired t-test with  $\alpha$  =0.05.

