We have not based the samples size upon the secondary exploratory hypotheses, however, the effect sizes that can be detected with our sample size of 22 subjects can be estimated. For the MBT method, the sample size is based upon our previous experience in CF with detecting differences in Cmax and AUC for HA and the HA/PA ratio4, and in detecting the percent change in HA absorption (from pharmacokinetic modeling) compared to healthy subjects5. For our proposed study, with the crossover design, 22 subjects (11 in each randomization group) will have 80% power to detect a difference in means of 0.60 (the difference in Cmax (in AUC) HA/PA ratio, with a mean of 1.62 (1.30) for omeprazole treatment, compared to 1.02 (0.70)) for placebo: this is a 37% increase in Cmax and 46% increase in AUC with omeprazole treatment compared to placebo, assuming that the common SD is 0.68 using a paired t-test with  $\alpha$  =0.05. For the CFQ-R domain scores, a sample size of 22 subjects with provide 80% to see an increase of 9 points (i.e. from 80 to 89) with omeprazole treatment compared to placebo with a common SD of 15 points using a paired t-test with  $\alpha$ =0.05. For the SmartPill®, Gelfond has demonstrated significantly lower duodenal pH in subjects with CF compared to healthy controls. The outcome of interest is the time that it takes for the pH to reach 5.5, the minimum level required to dissolve the enteric coating from PERT so that they are effective for nutrient absorption. In a study of 10 subjects with CF compared to 10 healthy controls using the SmartPill® methodology, the time required to reach a pH of 5.5 in CF was 17.7±6.8 compared to  $6.3\pm6.4$  In controls (p=0.004). We expect a subsample of 12 subjects to be 18+ years of age and use the SmartPill® for duodenal pH assessment. A sample of 10 subjects is required for 80% power to see a reduction in time to pH of 5.5 in the GI tract from 17 to 11 minutes

with omeprazole treatment compared to placebo, with a common SD of 7 minutes, using a paired t-test with  $\alpha$ =0.05.

Using this randomized crossover design, a total sample of 22 subjects, 11 in each randomization group will be needed. Therefore, enrolling 24 subjects (12 in each group) will result in 22 subjects completing the study if we experience 10% attrition.

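### The on/off comparison of CFA% that the trial is powered on ignores period; the between-sequence comparison of change, already in the plan, should be named primary

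*Combined protocol and SAP*

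**What the plan says.** The design is a two-treatment, two-period crossover, and randomization decides only which treatment comes first (9.1.1). The primary outcome is measured twice: "the coefficient of fat absorption (CFA%) will be determined by the 72-hour stool collections at Visits 2 and 3" (5.2.1).

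- **6.3.2 Efficacy Analysis**, for the total group: "Significance of the differences on and off treatment assessed with paired t tests or Wilcoxon sign rank tests as appropriate". No single test is labelled primary.
- **6.4 Sample Size and Power** takes a 3-point gain on omeprazole "compared to no change (0%) when on placebo with a common SD of 5% using a paired t-test", with 22 completers. This makes the paired t-test the intended primary test in effect.
- **6.3.1 Baseline Data**: "Differences between randomization groups at each time point and differences in the change over time with treatment will be assessed with unpaired t tests", with Mann-Whitney as the alternative. The Statistical And Analytic Plan row of the synopsis repeats it: "differences in the change over time with treatment will be assessed with unpaired t tests".
- The mixed model in 6.3.2 is for subject characteristics and names no period or sequence term. A period effect is not mentioned anywhere in the plan.

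**The concern.** In a crossover, everything that changes between the first and second assessment falls on omeprazole in one sequence and on placebo in the other. A paired test pools the on-minus-off differences from both sequences as one sample. A period effect then shifts the two sequences in opposite directions and is counted as random variation. If completers are unequal between sequences, part of it also enters the estimate.

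A period effect is possible here. Visit 2 is each subject's first home stool collection and weighed food record in the study, and Visit 3 is the second. Subjects already on acid suppression come off it only before period 1 (3.1.2, 9.4.2). At stake are power and interval width in a trial with 22 completers, and a small bias if dropout is one-sided.

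The plan does not lack the right analysis. CFA% has no measurement before Visit 2, so its change over time must be Visit 3 minus Visit 2, and the unpaired comparison of that change between sequences cancels the period effect. The gap is that this test sits under Baseline Data without any status.

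**Working it through.** **Inputs.** Treatment effect δ = 3, SD 5, α = 0.05 and 22 completers as 11 + 11 (6.4). Two-sided testing is assumed, since the plan does not state sidedness. The period effect π (period 2 minus period 1) is assumed to lie between 0 and 3 points, because the documents give none.

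The SD of the on-minus-off difference is taken at three values:
- 5, reading the common SD as the SD of differences;
- 3.0, the only SD of within-subject CFA% change in the documents, for another drug: "there was a significant increase in CFA% of 3.1±3.0% (p<0.01) with ivacaftor treatment" (6.4);
- 7.07 = 5 × √2, reading 5 as the SD within each period with zero correlation.

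**The plan's own figure.** Normal approximation: n = ((1.960 + 0.842) × 5/3)² = 21.8, so 22, with power 80.35%. This matches 6.4 and shows that SD 5 was used as the SD of differences. The exact paired t-test at n = 22 has 76.5% power. That shortfall is a separate matter; the comparison below uses exact power for both tests.

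**Paired test.** The on-minus-off difference has mean δ − π in the omeprazole-first sequence (n₁ subjects) and δ + π in the placebo-first sequence (n₂ subjects), with n = n₁ + n₂.
- Bias of the paired mean = π(n₂ − n₁)/n. This is zero at 11/11.
- The residual sum of squares is SD² times a noncentral chi-square on n − 1 = 21 df, with noncentrality 4π²n₁n₂/(n·SD²). At 11/11, π = 2 and SD 5, this is 4 × 4 × 121/(22 × 25) = 3.52. The expected variance is then 25 × (21 + 3.52)/21 = 29.2 instead of 25.
- Power, type I error and mean CI width follow by numerical integration.

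**Adjusted test.** Half the between-sequence difference in Visit 3 minus Visit 2 has mean δ whatever π is. Its SE = (SD/2)√(1/n₁ + 1/n₂) = 2.5 × √(2/11) = 1.066, and its noncentrality is 3/1.066 = 2.81 on 20 df. Power is 76.3% and mean CI width 4.39.

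**Results at 11/11, SD 5**

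| π | Paired power | Adjusted power | Paired type I error | Paired CI width (adjusted 4.39) |
|---|---|---|---|---|
| 0 | 76.5% | 76.3% | 5.0% | – |
| 0.5 | 76.2% | 76.3% | – | – |
| 1 | 75.2% | 76.3% | 4.6% | 4.47 (2% wider) |
| 2 | 71.3% | 76.3% | 3.5% | 4.74 (8% wider) |
| 3 | 64.7% | 76.3% | 2.3% | 5.15 (17% wider) |

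**Other SDs at 11/11, π = 1, 2, 3**
- SD 3.0: paired 99.1%, 98.0%, 94.7%; adjusted 99.4%.
- SD 7.07: paired 46.8%, 44.4%, 40.7%; adjusted 47.4%.

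The adjusted test has more power once π exceeds about 0.3 points (SD 3.0), 0.4 (SD 5) or 0.5 (SD 7.07).

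**Unequal completers.** Section 6.4 expects that "enrolling 24 subjects (12 in each group) will result in 22 subjects completing the study if we experience 10% attrition". If both dropouts come from one sequence the split is 12/10, the most unequal possible for 22 completers. At SD 5:
- π = 1: bias 1 × 2/22 = 0.09 in either direction; paired power 72.6% or 77.7%.
- π = 2: bias 2 × 2/22 = 0.18 in either direction; paired power 65.6% or 76.6%.
- Adjusted power is 76.0% throughout, without bias.

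Paired power above 76.0% here comes partly from bias towards omeprazole.

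**Rank versions** (simulated, 11/11, SD 5, π = 0, 1, 2, 3): signed-rank 73.7%, 72.1%, 67.6%, 60.3%; Mann-Whitney on the change 73.2%, 73.1%, 73.0%, 73.2%.

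**The case against.** The strongest reply is that no invalid conclusion has been shown. At 11/11 the paired estimate is unbiased and the test conservative. Even at 12/10 its type I error stays below 5% (4.7%, 3.8% and 2.7% at 1, 2 and 3 points), and a bias of 0.18 is small against a target of 3. The period effect is assumed, and the top of the range equals the whole hypothesised treatment effect. The design also works against a large one: a lead-in of 14 days precedes period 1, a "14-day washout period during which subjects will discontinue their study medication but continue their standard diet/PERT use" precedes period 2 (3.1.3), and the two assessments are identical (4.2). At 1 point the gain is only 1.1 power points, and at SD 3.0 the paired test keeps at least 94.7% power.

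All of that stands, and it limits the claim to efficiency plus protection against a small bias. It is also true that the plan neither labels a primary test nor writes out Visit 3 minus Visit 2. Both are inferences, from the test used for power and from when CFA% is measured. None of this favours keeping the paired test: its best case is an advantage of 0.2 power points at 11/11, and its losses grow with any real period effect.

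**Conclusion.** The concern holds as a matter of which test should be primary; no analysis is missing from the plan. At SD 5 with equal completers, an unmodelled period effect of 1 to 3 points costs the paired t-test 1.1 to 11.6 power points (76.3 − 75.2 and 76.3 − 64.7) and widens its interval by 2% to 17%. At 12/10, a 2-point period effect adds a bias of 0.18 points in either direction. With no period effect nothing is gained. These sizes rest on the assumed period effects, two-sided testing and the chosen SD of differences. Neither test removes carryover. The change is worth making because it costs almost nothing, although no bias is known to exist.

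**What to change.** In 6.3.2, name one primary analysis of CFA%: the Visit 3 minus Visit 2 change compared between the two randomized sequences by unpaired t-test at two-sided 0.05. Halve the between-sequence difference (placebo-first minus omeprazole-first) and its confidence limits, so that the result is the omeprazole-minus-placebo difference with a 95% CI. With complete data, a linear model with treatment, period and subject gives the same estimate and p-value and may be specified instead. Use the Mann-Whitney comparison of the change, also already listed, as the sensitivity analysis. Label the simple paired, within-group and by-visit CFA% tests supportive or descriptive.

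Align 6.4, the sentence in 6.3.1 and the synopsis with this choice. On the plan's own normal formula the required number stays at 22, with the same 80.35% power.

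The cost is wording and one degree of freedom: at SD 5 with no period effect, about 0.2 power points at 11/11 (76.5% to 76.3%) and 0.6 at 12/10 (76.54% to 75.99%). No subject, visit or sample is added.

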## **Secondary Hypotheses:**

In a subset of subjects (≥18 years), PPI in combination with PERT will increase duodenal pH compared to placebo as indicated by the SmartPill®.

	
 
PPI in combination with PERT will increase dietary fat absorption compared with placebo as indicated by the MBT.
 

	
 
Improvement in dietary fat absorption will be associated with improvements in quality of life and nutritional status measures.
 

Test Article(s) (If Applicable)	Omeprazole, a commonly-prescribed proton pump inhibitor, used with the patient's current pancreatic enzyme replacement therapy
Study Design	This is a randomized placebo-controlled double-blinded trial with a crossover design to determine the efficacy of omeprazole as an adjunct to PERT to improve dietary fat absorption in 24 adolescent (≥12 years) and adult subjects with CF and EPI.
Subject Population	Inclusion Criteria
Key criteria for Inclusion and Exclusion:	
 
Cystic fibrosis and pancreatic insufficiency (Fecal elastase <200 ug/g stool)
 

	2. Age ≥12 years
	3. In usual state of good health
	
 
Willingness to participate in a four-month study with three visits
 

	
 
MBT Quality Improvement Project
 

	
 
Two Healthy Adults
 

	Exclusion Criteria
	5. FEV1 <40% predicted
	6. Pregnancy or breast feeding
	7. Other illness affecting growth or nutritional status
	

Unwillingness to continue their clinically established PERT dose for the duration of the study

	9. Use of other medication that affects dietary fat absorption
	10. Allergy to soy products
	11. Allergy to safflower products (microlipids)
	12. For subjects ≥18 years, celiac disease or allergy to gluten
	MBT Quality Improvement Project
	
 
Pregnancy or breast feeding
 

	
 
Use of other medication that affects dietary fat absorption
 

	
 
Allergy to soy products
 

Number Of Subjects	24 subjects

Study Duration	Duration from consent to completion of the study for each subject is approximately 100 days.
	The entire study is expected to last two years.
Study Phases	Screening (Visit 1): Screening for eligibility and obtaining consent. Once consented, PPI dose will standardized and subjects will be randomized. Standardization of diet and PERT that will continue throughout the study
	Intervention : Subjects are given either placebo or omeprazole to take for 28 days.

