## 2 STUDY OBJECTIVES

2.1 The purpose of the study is to determine if a proton-pump inhibitor will improve the efficacy of pancreatic enzyme replacement therapy as evidenced by changes in

fat absorption and to characterize the mechanism by which this improvement occurs. Primary Objective (or Aim)

2.2 The primary objective of this study is to determine if a proton-pump inhibitor improves fat malabsorption in subjects with CF and EPI who are on pancreatic enzyme replacement therapy. The primary outcome measure of fat absorption will be the gold standard coefficient of fat absorption (CFA). Secondary Objectives (or Aim)

The secondary objectives are to:

- Determine if changes in duodenal pH on and off acid suppression occur using the SmartPill®, and if such changes correlate with changes in fat absorption.
- Characterize changes in triglyceride absorption on and off acid suppression using the malabsorption blood test.
- Explore associations among changes in nutrition status (weight, height, BMI), GI symptoms, and quality of life in subjects treated with omeprazole vs. placebo in combination with PERT.

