## 3.1.1 Screening Phase

Subjects will be recruited from the CF Centers at the Children's Hospital of Philadelphia (CHOP), hospitals affiliated with University of Pennsylvania, and other regional CF Centers. Potential subjects will be screened using the protocol inclusion and exclusion criteria. Twenty-four subjects with CF and EPI, 12 years of age and older, will be recruited, with a goal of 50% of subjects between the ages of 12 and 18. Subjects who are receiving PPI or H2 medication will be eligible, but must be willing to discontinue this medication use as needed to comply with the protocol. Subject or parent/guardian informed consent and, if applicable, child assent, will be obtained prior to any study-related procedures being performed, including discontinuation of current therapy. A stool sample will be collected to confirm eligibility based on exocrine pancreatic insufficiency as measured indirectly by fecal elastase if a fecal elastase has not already been documented in the medical record. Height and weight will also be obtained as a baseline. Subjects will be asked to follow a moderate to high fat diet and also to continue their clinically-established standard PERT dose for the duration of the study.

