## 4 STUDY PROCEDURES

## 4.1 Consent Visit (Visit 1)

- Review of health history including prior and concomitant medications
- Review demographics
- Informed Consent
- Review of diet pattern
- Subjects asked to maintain a moderate to high fat diet throughout the study
- Subjects asked to maintain their clinically established PERT dose throughout the study
- Subjects asked to wean PPI or H2-receptor antagonist medication, if taking
- Simple anthropometrics
- Stool collection if needed
- Sexual maturity self-assessment (age <18y, n=12)

- GI symptom questionnaire
- Urine pregnancy test (female subjects)
- Distribute arm 1 study medication

Protocol	Day 1	Da	ys 2-15			Day	/s 16-43					
Visit 1: Consent and Randomization	- Clarify diet & PERT - Questionnaires - Elastase (if needed)			l-day washout p RA medication, i Istain on standar h fat diet onfirm standardi	f applicable rd moderate	to	- Randomized treatment to either omeprazole (PPI) or placebo for 28 days					
	Day 44	Day 45		Day 46	Day 47	Day	48	Day 49	Day 50	Days 51-		
Visit 2: After 28-day treatment with PPI or placebo	- Fast from 8pm - No dairy - Remain on standard PERT	- MBT - 7am-4p - Serum la - Anthros  If ≥18 yea - SmartPil - Fast fror 12am	bs a rs: ll	- Resume moderate- high fat diet If ≥18 years: - SmartPill at 8am - 6hr fast	- Diet record (day 1)	- Die reco (day - 72 Stoo (day	ord v 2) -hr ol	- Diet record (day 3) - 72-hr Stool (day 2)	-72-hr Stool (day 3)	- 14-day washout period from treatment placebo		

	Days 65-92	2 – Randomized	crossover treatn	nent (PPI to p	lacebo, or pla	acebo to PPI)	for 28 days	
	Day 93	Day 94	Day 95	Day 96	Day 97	Day 98	Day 99	Day 100
Visit 3:  After 28-day crossover treatment with placebo or PPI	- Fast from 8pm - No dairy - Remain on standard PEM	-MBT - 7am-4pm -Serum labs - Anthros  If ≥18 years: - SmartPill - Fast from 12am	- Resume moderate- high fat diet If ≥18 years: - SmartPill at 8am - 6hr fast	- Diet record (day 1)	-Diet record (day 2) - 72-hr Stool (day 1)	-Diet record (day 3) - 72-hr Stool (day 2)	-72-hr Stool (day 3)	- Return to usual care and medication regimen - Return to usual diet

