## 6.2 Secondary Endpoints

The secondary objectives are exploratory, 1) to determine if changes in duodenal pH on and off acid suppression occur using the SmartPill®, and if such changes correlate with changes in fat absorption; 2) to characterize changes in triglyceride absorption on and off acid suppression using the MBT; 3) to explore associations among changes in nutrition status (weight, height, BMI), GI symptoms, and quality of life in subjects treated with omeprazole vs. placebo in combination with PERT.

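### The one association model names an exposure and population the trial does not have and, separately, no stated analysis relates within-subject changes to each other as the secondary aims require

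*Combined protocol and SAP*

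**What the plan says.** **The aims.** Three statements concern change against change.
- The objectives in section 2, repeated in 6.2, ask whether duodenal pH changes on and off acid suppression, "and if such changes correlate with changes in fat absorption".
- The synopsis lists as a secondary hypothesis: "Improvement in dietary fat absorption will be associated with improvements in quality of life and nutritional status measures".
- Sections 2 and 6.2 also plan to explore how changes in weight, height and BMI, GI symptoms and quality of life go together.

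Section 6.2 labels the secondary objectives exploratory.

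**The analyses.** Section 6.3.2 gives paired tests of each outcome on and off omeprazole, unpaired tests between randomization groups, an optional population PK model, and one association model: "A mixed-effects modeling approach will be employed to examine the correlation of subject characteristics (age, BMI, sex, disease status, etc) to CFA"%, and to duodenal pH, quality of life and the PA and HA exposure metrics. Its stated purpose is "to assess change over time in MBT response to PERT administration in subjects with CP". The synopsis uses the same purpose wording but omits quality of life from the outcomes.

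**Exposure and population.** The primary objective is "to determine if a proton-pump inhibitor improves fat malabsorption in subjects with CF and EPI who are on pancreatic enzyme replacement therapy". Subjects are to "continue their clinically-established standard PERT dose for the duration of the study" (section 3.1.1), and section 4.1 repeats this.

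**The concern.** There are two separate faults. First, the model's purpose clause describes a response to PERT in a population abbreviated CP. PERT is background treatment here, so the data contain no planned PERT contrast. CP is not in the abbreviation list.

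Second, the aims about linked changes have no matching analysis. The pH question is the mechanism question that section 2 gives as part of the study's purpose, and the adult subset undergoes two SmartPill studies to inform it. If nothing is specified, the analysis will be chosen after the data are seen. Alternatively, a coefficient linking BMI to CFA across subjects might be offered as support for the hypothesis about improvements, although it answers a different question.

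**Working it through.** **1. Aims set against analyses**

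| Stated aim | Closest analysis in the synopsis or 6.3.2 | Relates change to change? |
|---|---|---|
| pH change with CFA change | Separate on/off tests of pH and of CFA | No |
| CFA improvement with quality-of-life improvement | Separate on/off tests of CFA and of quality of life | No |
| CFA improvement with nutritional improvement | BMI as a subject characteristic in the model for CFA values | No |
| Changes in nutrition, GI symptoms and quality of life together | None; weight, height and GI symptoms are named in no efficacy analysis | No |

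The purpose clause mentions change over time only for the MBT response. The sentence after it compares metrics on and off omeprazole, but one metric at a time.

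**2. Why values cannot replace changes**

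Assume, for illustration, a between-subject SD of 10 and an SD of the on-off difference of 5 for both measures. The within-subject variance per visit is 5²/2 = 12.5 and the total variance is 100 + 12.5 = 112.5.
- Between-subject correlation 0.6, within-subject 0: correlation of values = 0.6 × 100/112.5 = 0.53; correlation of changes = 0.
- Between-subject 0, within-subject 0.6: correlation of values = 0.6 × 12.5/112.5 = 0.07; correlation of changes = 0.60.

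Simulation gave the same results (0.53 and 0.00; 0.07 and 0.60). Values can therefore show a clear association when changes show none, and the reverse.

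**3. How often a between-subject link would appear in the planned model**

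Inputs: 22 subjects and two visits; CFA SD 7.4 (sections 6.1 and 6.4, gating-mutation study); SD of differences 5 (section 6.4, reading its common SD that way). Assumed, because the documents give no figure: BMI SD 3 between subjects and 0.3 within, and no within-subject association. The model is a random-intercept model with a period term and BMI as predictor of CFA.

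| Between-subject correlation (assumed) | BMI coefficient with p<0.05 |
|---|---|
| 0 | about 5-6% |
| 0.3 | 27-30% |
| 0.5 | 63-66% |
| 0.7 | 94-95% |

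Ranges are over repeated runs. Regressing within-subject differences on each other with a sequence term gave about 4-6%. The percentages in the last three rows are the chance of detecting a true between-subject association. They are not error rates of the planned model. They show how readily such a result could arise and be misread as a within-subject one.

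**4. What an analysis of changes could detect**

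Fisher z, two-sided 0.05, 80% power: smallest r = tanh[(1.960 + 0.842)/√(n − 3)].
- n = 22: tanh(2.802/√19) = 0.57
- n = 12: tanh(2.802/√9) = 0.73
- n = 10: tanh(2.802/√7) = 0.79

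Here 22 is the evaluable sample in section 6.4, 12 the expected SmartPill subset, and 10 the number in its power statement. Simulation at the first two values gave power of 82% and 83%, so the approximation is slightly cautious. At a true r of 0.5 (assumed), power is about 67%, 38% and 31% for n = 22, 12 and 10. Adjusting for sequence replaces n − 3 by n − 4 and raises the detectable values to tanh(2.802/√18) = 0.58, tanh(2.802/√8) = 0.76 and tanh(2.802/√6) = 0.82.

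**The case against.** The best defence is that this is a wording slip plus missing detail in exploratory aims. CP looks like a typing error or carried-over text. The next sentence of 6.3.2 names the on/off omeprazole contrast, and it is unlikely that anyone would fit a PERT effect. Section 6.4 says the sample size was not based on the secondary hypotheses, and power for an analysis of changes is low. The planned model is also legitimate for what it says it does, which is to relate characteristics to outcomes.

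Much of this stands, and it rules out three stronger readings that a reader might infer.
- That the PERT and CP wording is why the aims go untested. It is not: correcting both words leaves the gap in place.
- That the plan has no omeprazole contrast for these outcomes. On/off tests are stated for CFA, pH, MBT and quality of life.
- That the percentages in step 3 are false-positive rates, or that the protocol intends to use the BMI coefficient as its test of the hypothesis. The documents do not say so; BMI is one example in an open list of characteristics.

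The gap itself is not answered. Exploratory status does not leave a listed hypothesis without need of an analysis, and 6.3.2 applies p<0.05 throughout without setting exploratory tests apart. Low power is a reason to report intervals; it does not justify leaving the analysis unspecified.

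**Conclusion.** The point holds in two separate parts. The association model's purpose clause, in the synopsis and in 6.3.2, names a contrast that the design holds constant and a population abbreviation that the document never defines. Independently, none of the stated change-with-change aims has an analysis, and a model of pooled values would mainly reflect between-subject association. The wording fault and the gap both rest on the text alone. The step 3 percentages rest on assumed BMI variation and correlations; the detectable correlations rest on approximate normality and on 22 and 10 to 12 complete pairs.

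The consequence is moderate. It affects what can be claimed about mechanism and about quality of life and nutrition. It does not affect the primary CFA analysis. The pH-CFA link is a stated objective but not a listed hypothesis, and it has the fewest subjects.

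**What to change.** In the synopsis statistical plan and in 6.3.2:

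1. Replace PERT administration with omeprazole versus placebo, and CP with CF, in the model's purpose clause.
2. Add, labelled exploratory, analyses of each subject's omeprazole-minus-placebo difference:
   - in the adult SmartPill subset, the CFA difference on the difference in the SmartPill pH outcome (section 6.4 names time to reach pH 5.5; state whether this is the one used);
   - in all evaluable subjects, the differences in CFQ-R scores, GI-symptom scores and weight or BMI on the CFA difference.
3. Adjust for sequence where numbers allow, so that a period effect shared by both measures does not create an association. Report a slope or correlation with its 95% confidence interval. A plain correlation of paired differences is a reasonable alternative in the smallest subset.
4. State that with about 22 and 10 to 12 subjects only correlations of about 0.57 and 0.73 to 0.79 are detectable with 80% power, and somewhat larger ones after adjustment for sequence.
5. If the model of characteristics is kept, say that it describes between-subject association and is not the test of the secondary hypothesis.

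The cost is a few sentences and regressions on data already to be collected, with no change to visits, sample size or primary analysis. The downside is wider intervals than a pooled model of values would give, and one degree of freedom for sequence, which matters most in the SmartPill subset.
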